## **7.2 Adverse Event Recording and Reporting**

Reporting participating investigators will assess the occurrence of AEs and SAEs at all participant evaluation time points during the study. All AEs and SAEs whether reported by the participant, discovered during questioning, directly observed, or detected by physical examination, laboratory test or other means, will be recorded in the participant’s medical record and on the appropriate study-specific case report forms. All AEs must be recorded in the participant’s medical record, stating the duration and intensity of the event, action taken by the investigator and outcome of the event. The investigator must evaluate the causal relationship between the study drug(s) and the adverse event.

The investigator must evaluate all abnormal laboratory results to determine the clinical significance.

All AEs detected by the investigator or by the participant must be recorded on the appropriate study-specific CRFs, stating the duration and intensity of the event, action taken by the investigator and outcome of the event. The investigator must evaluate the causal relationship for each AE.

The descriptions and grading scales found in the CTEP Version 5.0 of the NCI Common Terminology Criteria for Adverse Events (CTCAE) will be utilized for AE reporting. The CTEP Version 5.0 of the CTCAE is identified and located on the CTEP website at:  
[http://ctep.cancer.gov/protocolDevelopment/electronic\\_applications/ctc.htm](http://ctep.cancer.gov/protocolDevelopment/electronic_applications/ctc.htm)

Each adverse event will be assessed to determine if it meets the criteria for SAE reporting. If an SAE occurs, expedited reporting will follow local policies and regulations as appropriate. Hematologic adverse events will be recorded/reported only if >grade 2 or if an action on study drug was required. These events should be captured on the adverse event pages of the CRF only.

## **7.3 Reporting Requirements**

For multi-site trials where a DF/HCC investigator is serving as the sponsor, each participating investigator is required to abide by the reporting requirements set by the DF/HCC. The study must

be conducted in compliance with FDA regulations, local safety reporting requirements, and reporting requirements of the Principal Investigator/Sponsor.

Each investigative site will be responsible to report SAEs that occur at that institution to their respective IRB. It is the responsibility of each participating investigator to report serious adverse events to the Principal Investigator/Sponsor, the participating site's IRB, and others as described below.

## 7.4 Reporting to the Study Sponsor

### Serious Adverse Event Reporting

The lead site will be responsible for SAE reporting to the pharmaceutical partners (including SUSAR events). The lead site will report all reports/outcomes associated to pregnancy or lactation exposure to the pharmaceutical partners.

If a patient experiences an SAE after signing informed consent, but prior to receiving study drug, the event will NOT be collected unless the investigator feels the event may have been caused by a protocol procedure. All serious adverse events that are related to study drug and occur \ during treatment or within 30 days of the last dose of treatment, with the exception of participants who withdraw from treatment, in whom adverse events will be collected until 60 days following the last treatment administration. All DF/HCC Reportable Adverse Events must be reported to the study sponsors within 1 working day. This includes the following:

- Grade 2 (moderate) and Grade 3 (severe) events that are unexpected and at least possibly related/associated with the intervention.  
**Note:** Grade 2 and Grade 3 lab abnormalities that are considered by the investigator to be clinically insignificant and do not require therapy, or adjustment in prior therapy, do not need to be reported.
- All Grade 4 (life-threatening or disabling) events that are unexpected or not specifically listed in the protocol as not requiring reporting.
- All Grade 5 (fatal) events while the participant is enrolled and actively participating in the trial OR when the event occurs within 30 days of the last study intervention.

Note, if the participant is in long term follow up, report the death at the time of continuing review.

Due to the additional expedited reporting criteria, the table below is a tool to summarize the reporting requirements and timelines for SAEs and DF/HCC reportable adverse events.

Attribution	SAEs	DF/HCC Reportable AEs				
	All SAEs (section 7.1)	Gr. 2 & 3 AE Expected #	Gr. 2 & 3 AE Unexpected #	Gr. 4 AE Expected #	Gr. 4 AE Unexpected #	Gr. 5 AE Expected or Unexpected
Unrelated Unlikely	24 hours	Not required	Not required	5 calendar days*	5 calendar days	24 hours
Possible Probable Definite	24 hours	Not required	5 calendar days	5 calendar days*	5 calendar days	24 hours

# If event meets SAE criteria listed in section 7.1 in addition to grade, attribution and expectedness, event must be reported within 24 hours.

\* If listed in protocol as expected and not requiring reporting, event does not need to be reported.

Participating investigators must report each serious and/or DF/HCC reportable adverse event in accordance with the table above using the MEDWATCH FDA Form 3500A form or local IRB report form. In the event that the participating investigator does not become aware of the serious adverse event immediately (e.g., participant sought treatment elsewhere) or within the time frames listed in the table above, the participating investigator is to report the event within 24 hours after learning of it and document the time of his or her first awareness of the adverse event.

The Overall PI will submit AE reports from outside institutions to the DFCI OHRS according to DFCI IRB policies and procedures in reporting adverse events.

### **Non-Serious Adverse Event Reporting**

Non-serious adverse events will be reported on the adverse event Case Report Form.

### **7.5 Reporting to the Food and Drug Administration (FDA)**

The Overall PI, as study sponsor, will be responsible for all communications with the FDA. The Overall PI will report to the FDA, regardless of the site of occurrence, any serious adverse event that meets the FDA's criteria for expedited reporting following the reporting requirements and timelines set by the FDA.

### **7.6 Reporting to Hospital Risk Management**

Participating investigators will report to their local Risk Management office any participant safety reports, sentinel events or unanticipated problems that require reporting per institutional policy.

### **7.7 Routine Adverse Event Reporting**

All Adverse Events **must** be reported in routine study data submissions to the Overall PI on the toxicity case report forms. **AEs reported through expedited processes (e.g., reported to the Institutional Review Board (IRB), FDA, etc.) must also be reported in routine study data submissions.**

### 8. STUDY CALENDAR

Baseline evaluations are to be conducted within 28 days prior to start of protocol therapy. Scans and x-rays must be done  $\leq 4$  weeks prior to the start of therapy. In the event that the participant's condition is deteriorating, laboratory evaluations should be repeated within 48 hours prior to initiation of the next cycle of therapy.

Assessments must be performed prior to administration of any study agent. Study assessments and agents should be administered within  $\pm 8$  days of the protocol-specified date, unless otherwise noted.

**Table 12 Treatment Schedule-Representative Cycle for Induction Phase**

Study treatment	Days																												
	1	2	3	4	5	6	7	8	9	10	11	12	13	14	15	16	17	18	19	20	21	22	23	24	25	26	27	28	
Lenalidomide	X	X	X	X	X	X	X	X	X	X	X	X	X	X	X	X	X	X	X	X	X								
Carfilzomib	X							X						X															
Isatuximab a	X							X						X								X							
Dexamethasone	X	X						X	X						X	X							X	X					

a - IV every week (Q1W) for 8 weeks, then every 2 weeks (Q2W) for 16 weeks, thereafter, every 4 weeks (Q4W). Note that this table is a representative cycle for the induction phase in the first 8 weeks.

**Table 13 Treatment Schedule-Representative Cycle for Maintenance Phase**

Study treatment	Days																												
	1	2	3	4	5	6	7	8	9	10	11	12	13	14	15	16	17	18	19	20	21	22	23	24	25	26	27	28	
Lenalidomide	X	X	X	X	X	X	X	X	X	X	X	X	X	X	X	X	X	X	X	X	X	X							
Carfilzomib a	X														X														
Isatuximab a	X																												

a – Carfilzomib and isatuximab for high-risk patients only; lenalidomide alone for standard-risk. Isatuximab will discontinue after completing two years of maintenance.

In the maintenance phase, dexamethasone 20mg PO or IV will be administered to patients as a pre-infusion medication prior to isatuximab dosing.

**Table 14: Schedule of Assessments**

Table 14A: KRDI with Autologous Stem Cell Transplant

	Screening (Within 28 days prior to registration) 	Induction Phase				Maintenance Phase (Cycles 7+)	At treatment discontinuation (30 [d ± 7] days after last dose)	Follow up  (Every 12 ± 3 weeks)
		Treatment Phase (Cycles 1-2)	Treatment Phase (Cycles 3-4)	Auto-SCT	Consolidation Phase (Cycles 5-6)			
Procedures (± 8-day window for obtaining all assessments)								
Informed consent 								
Demographics/Medical History	X							X
ECOG Performance Status	X	X	X		X	X	X	X
12 lead ECG	X							
Physical Examination including height and weight 	X	X	X		X	X	X	X
Vital Signs (temperature, heart rate, blood pressure) 	X	X	X		X	X	X	X
AE evaluation		X	X		X	X	X	
Blood type/indirect antiglobulin test	X							
Pulmonary Function Test FEV1 	X							
Bone Marrow Biopsy 	X	After 4 cycles, at the completion of consolidation, and after 24 cycles (± 3 weeks) if sCR or CR maintained (including subjects with VGPR or better and suspected isatuximab interference)					X 	
Laboratory Assessments								
CBC with diff 	X	D1, 8, 15, 22	D1, 15		D1, 15	X	X	X
Serum Chemistries 	X	D1, 8, 15, 22	D1, 15		D1, 15	X	X	X
Creatinine Clearance 	X	D1, 8, 15, 22	D1, 15		D1, 15	X	X	
SPEP, IFE, B2M	X	X	X		X	X	X	X
Free light chain testing	X	X	X		X	X	X	X
UPEP 	X	X	X 		X 	X 	X 	X 
24-hour urine, protein, creatinine 	X	X	X 		X 	X 	X 	
Pregnancy Test 	X	X	X		X	X	X	
Interference Testing 	X	X	X		X	X	X	
MRD (aspirate) 		After 4 cycles, at completion of consolidation, and after 24 cycles (± 3 weeks) if sCR or CR maintained (including subjects with VGPR or better and suspected isatuximab interference)						
Imaging Assessments								

Skeletal Survey 	X							
Extramedullary Plasmacytoma 	X							
DXA 	X					X		
Quality of Life Assessments								
EORTC-QLQ-C30		X	X		X	X	X	
EORTC-QLQ-MY20		X	X		X	X	X	

Table 14B: KRDI with Transplant-Deferred

	Screening (Within 28 days prior to registration) 	Induction Phase		Maintenance Phase (Cycles 9+)	At treatment discontinuation (30 [d ± 7] days after last dose)	Follow up  (Every 12 ± 3 weeks)	
		Treatment Phase (Cycles 1-2)	Treatment Phase (Cycles 3-8)				
		Procedures (± 8-day window for obtaining all assessments)					
Informed consent 							
Demographics/Medical History	X					X	
ECOG Performance Status	X	X	X	X	X	X	
12 lead ECG	X						
Physical Examination including height and weight 	X	X	X	X	X	X	
Vital Signs (temperature, heart rate, blood pressure) 	X	X	X	X	X	X	
AE evaluation		X	X	X	X		
Blood type/indirect antiglobulin test	X						
Pulmonary Function Test FEV1 	X						
Bone Marrow Biopsy 	X	After 4 cycles, at the completion of induction, and after 24 cycles (± 3 weeks) if sCR or CR maintained (including subjects with VGPR or better and suspected isatuximab interference)			X 		
Laboratory Assessments							
CBC with diff 	X	D1, 8, 15, 22	D1, 15	X	X	X	
Serum Chemistries 	X	D1, 8, 15, 22	D1, 15	X	X	X	
Creatinine Clearance 	X	D1, 8, 15, 22	D1, 15	X	X		
SPEP, IFE, B2M	X	X	X	X	X	X	

Free light chain testing	X	X	X	X	X	X
UPEP 	X	X	X 	X 	X 	X 
24-hour urine, protein, creatinine 	X	X	X 	X 	X 	
Pregnancy Test 	X	X	X	X	X	
Interference Testing 	X	X	X	X	X	
MRD (aspirate) 	X	After 4 cycles, at the completion of induction, and after 24 cycles (± 3 weeks) if sCR or CR maintained (including subjects with VGPR or better and suspected isatuximab interference)			X 	
Imaging Assessments						
Skeletal Survey 	X					
Extramedullary Plasmacytoma 	X					
DXA 	X			X		
Quality of Life Assessments						
EORTC-QLQ-C30		X	X	X	X	
EORTC-QLQ-MY20		X	X	X	X	

Abbreviations: AE= adverse events; ANC= absolute neutrophil count; B2M=Beta2-Microglobulin; Cycle= each cycle is 28 Days.; DXA = dual-energy x-ray absorptiometry; IFE=Immunofixation; MRD = Minimal Residual Disease; SPEP= Serum protein electrophoresis, UPEP=Urine protein electrophoresis.

 ≤28 days prior to patient enrollment. Some pretreatment clinical laboratory values should be tested ≤14 days of registration.

 Informed consent must be obtained before any study assessments are performed unless it is standard of care.

 Physical examination: A routine physical examination by the investigator (or the designated physician will include height (screening only) and weight. Height will be measured only once at screening. Weight will be measured on every visit day. Actual weight on C1D1 should be used for initial dose calculation. If a subject's weight changes by more than 10% from C1D1, the dose of all study treatments should be re-calculated.

 Vital signs (temperature, pulse/heart rate, respiratory rate, and blood pressure) will be measured in sitting position. For all infusions except C1D1 (see note below), these should be measured immediately before the start of isatuximab infusion, prior to each infusion rate increase, and at the end of isatuximab infusion.

 Pulmonary function testing (spirometry) is required only for subjects with chronic obstructive pulmonary disease or asthma. FEV1 should be measured.

 Bone marrow biopsy and aspirate for morphology, immunohistochemistry, or immunofluorescence, cytogenetics- Fluorescent in situ hybridization (FISH), and karyotype. FISH testing to include del(17p), t(4;14), t(14;16), t(14;20), and 1q duplication. Bone marrow biopsy is recommended at the time of best response for confirmation of complete response.

 Bone marrow biopsy recommended at time of progression.

 CBC with differential: Complete blood count with differential (includes white blood cells, red blood cells, platelets, ANC, lymphocyte and hemoglobin).

 Serum chemistries: To include sodium, potassium, chloride, bicarbonate, calcium, magnesium, phosphorus, blood urea, nitrogen, creatinine, glucose, albumin, total protein, alkaline phosphatase, total bilirubin, aspartate aminotransferase, alanine aminotransferase, lactate dehydrogenase, and uric acid.

 Creatinine clearance: Estimated glomerular filtration rate will be calculated using Cockcroft-Gault equation.

 Pregnancy test will be done at screening and once every cycle. Urine or serum HCG may be tested based on institutional preference.

 For all patients with VGPR, a positive serum IFE, and a negative SPEP and/or patients with an M-protein of  $\leq 0.02$  g/dL on SPEP and IgG kappa MM

 At all visits, during the bone marrow aspirate procedure, the first aspirate sample that is drawn will be sent to the central laboratory to determine MRD. All bone marrow aspirates to be sent to the central laboratory should be at least 5 mL. Any patient with a residual IgG kappa M-protein obtaining a VGPR be tested. There should also be a note that patient with a non-IgG kappa myeloma who have a measurable IgG kappa M-protein after treatment be tested as well. Additional bone marrow aspirate samples may be taken and used for local laboratory testing. MRD will be tested after 4 cycles, at the completion of induction, and after 24 cycles if CR maintained

 Skeletal Survey: Radiograph of skull, spine, chest, pelvis, upper extremities shoulder to elbow, lower extremities hip to knee.

 Clinical examination or MRI may be used (subjects with history; physical or radiologic examination, as applicable).

 DXA to be performed at baseline and at the completion of induction (transplant-deferred) or consolidation (post-SCT)

 24 hour urine & UPEP may be omitted after Cycle 2 if subjects disease is not followed by Urine M Protein. Except at time of suspected CR and sCR.

 The first follow up visit should occur three months after the end of treatment visit.

## **9.0 MEASUREMENT OF EFFECT**

### **9.1 International Myeloma Working Group (IMWG) Response Categories**

Disease evaluations will be performed at the completion of each cycle of treatment during the induction phase and then at the completion of every even cycle (14, 16, 20, etc.) during maintenance phase until disease progression.

Isatuximab detection on serum immunofixation electrophoresis (IFE) has been demonstrated in patients treated and may interfere with the traditional IMWG criteria of negative serum IFE for CR or sCR. To mitigate this interference, serum M-protein interference sampling will be performed.

For all patients with VGPR, a positive serum IFE, and a negative M-protein by serum protein electrophoresis (SPEP), reflex IFE testing will be performed to confirm the presence of isatuximab on IFE. In addition, patients who have an SPEP of  $\leq 0.2$  g/dL and IgG kappa MM, reflex testing will also be performed to determine whether the para-protein identified on SPEP/IFE is monoclonal isatuximab or the patient's endogenous myeloma protein.

### **IMWG Uniform Response Criteria + Definition of Minimal Response as Adopted from the EBMT Criteria**

The IMWG uniform response criteria will be used for determining response to therapy and progression of disease (Table 15). Source documentation for all biochemical and radiographic evaluations of disease will be collected for confirmation of response and disease progression.

**Table 15: IMWG Uniform Response Criteria**

Response Category	Response Criteria	Response Criteria for Disease Measurable by Serum FLC Testing Only
Complete Response (CR)	Negative serum immunofixation and 24-hour urine immunofixation, disappearance of all extramedullary plasmacytomas (if present at baseline) and <5% plasma cells on repeat bone marrow examination.	All other criteria for CR met + normal serum free light chain ratio.
Stringent Complete Response (sCR)	All criteria for CR must be met + normal serum free light chain ratio + absence of clonal plasma cells on bone marrow examination by immunohistochemistry or 2- to 4-color flow cytometry.	All other criteria for sCR met + normal serum free light chain ratio.
Very Good Partial Response (VGPR)	Serum and urine M-protein detectable on immunofixation testing but not on electrophoresis OR $\geq 90\%$ reduction in serum M-protein plus urine M-protein <100 mg/24 hours.	$\geq 90\%$ reduction in the difference between the involved and uninvolved serum free light chain level.
Partial Response (PR)	$\geq 50\%$ decrease in the serum M-protein + $\geq 90\%$ reduction in the urine M-protein OR to <200 mg/24 hours + $\geq 50\%$ reduction in the size of extramedullary plasmacytomas (if present at baseline).	$\geq 50\%$ reduction in the difference between the involved and uninvolved serum free light chain level.
Minimal Response (MR)	25% - 49% decrease in the serum M-protein + 50 – 89% reduction in the urine M-protein + 25% – 49% reduction in the size of extramedullary plasmacytomas (if present at baseline) + no increase in size or number of lytic bone lesions (development of compression fracture does not exclude response). a	
Stable Disease (SD)	Not meeting criteria for CR, sCR, VGPR, PR, MR, or PD	

Progressive Disease (PD)	
Increase of <math>\geq 25\%</math> from lowest response value (nadir)b in any of the following:
 

1) Serum M-protein (absolute increase must be <math>\geq 0.5</math> g/dL) AND/OR:

2) Urine M-protein (absolute increase must be <math>\geq 200</math> mg/24 hours) AND/OR:

3) For patients without a measurable serum or urine M-protein but measurable disease by serum free light chain testing: Difference between the involved and uninvolved serum free light chain level (absolute increase must be <math>\geq 10</math> mg/dL) AND/OR:

4) For patients without a measurable serum or urine M-component or serum free light chain level: % marrow involvement with myeloma (absolute increase must be <math>\geq 10\%</math>).

 
Definite development of new bone lesions or extramedullary plasmacytomas or definite increase in the size of existing bone lesions or extramedullary plasmacytomas.

--------------------------	---

a For patients who do not have measurable disease by M-protein measurement or serum free light chain levels but  $\geq 30\%$  involvement of the marrow at baseline, a  $\geq 50\%$  reduction of bone marrow involvement is required to meet criteria for a PR.

b The lowest response value (nadir) does not have to be a value that has been confirmed by repeat measurement.

## 9.2 Minimal Residual Disease Assessment

Minimal residual disease (MRD) assessment will be assessed by next generation sequencing in both blood and bone marrow aspirate whenever a bone marrow (BM) sample is obtained as described in (Table 16) at the time points mentioned in and the Schedule of Assessments. Please see the Appendix F for details of MRD collection and processing.

**Table 16: Bone Marrow Testing Requirements**

Sample	Local Laboratory Testing	Central Laboratory Testing
Screening aspirate and biopsy	Cytogenetics (FISH a ), morphology, immunohistochemistry, immunofluorescence, or flow cytometry	MRD: a portion of the BM aspirates (at least 5 mL) collected at screening will be sent to a central laboratory. If a fresh BM aspirate will not be performed at screening because a sample is available within 28 days prior to enrollment, then non-decalcified diagnostic tissue (BM aspirate smear or clot slides) should be collected for MRD assessment
Follow-up aspirate and/or biopsy	Morphology, immunohistochemistry, immunofluorescence, or flow cytometry	MRD: a portion of the BM aspirates (at least 5 mL) collected at screening will be sent to a central laboratory.
For response confirmation, additional BM aspirates or biopsies will be performed locally to confirm CR or sCR		
To confirm CR or sCR at any time (including patients with VGPR or better and suspected istuximab interference) immunohistochemistry, immunofluorescence (requires kappa/lambda ration from analysis of $\geq$ 100 cells) or 2- to 4- color flow cytometry		

aFISH- testing to include del(17p), t(4;14), t(14;16), t(14;20), and 1q duplication

## 9.3 Assessment of Lytic Bone Disease

A complete skeletal survey (including skull, entire vertebral column, pelvis, chest, humeri, femora, and any other bones for which the investigator suspects involvement by disease) is to be performed and evaluated by the local roentgenography during the screening phase. Magnetic resonance imaging and/or low dose computerized tomography (CT)-scan, and/or positron

emission tomography (PET)/CT fusion studies are acceptable methods for evaluation of bone disease and may be included at the discretion of the investigator. If an alternative imaging modality (MRI, CT, or PET/CT) was used prior to registration in addition to the complete skeletal survey, then both methods must be used to document disease status.

Sometimes subjects present with disease progression manifested by symptoms of pain due to bone changes. Therefore, disease progression may be documented, in these cases, by skeletal survey or other imaging studies, depending on the symptoms that the subject experiences. If the diagnosis of disease progression is obvious by radiographic investigations, then no repeat confirmatory x-rays are necessary. In instances where changes may be more subtle, a repeat x-ray may be needed in 1 to 3 weeks.

#### **9.4 Documentation of Extramedullary Plasmacytomas**

Sites of known extramedullary plasmacytomas must be documented prior to registration. Clinical examination or MRI may be used to document extramedullary sites of disease. Computed tomography scan evaluations are an acceptable alternative if there is no contraindication to the use of IV contrast. Positron emission tomography scan or ultrasound tests are not acceptable to document the size of extramedullary plasmacytomas. However, PET/CT fusion studies are acceptable.

Extramedullary plasmacytomas should be assessed for all subjects with a history of plasmacytomas, or if clinically indicated prior to registration, by clinical examination or radiologic imaging. Assessment of measurable sites of extramedullary disease will be performed and evaluated locally for subjects with a history of plasmacytomas or as clinically indicated during treatment until development of confirmed CR or confirmed disease progression. If assessment can only be performed radiologically, then evaluation of extramedullary plasmacytomas must be performed according to the Schedule of Assessments. For every subject, the methodology used for evaluation of each disease site should be consistent across all visits. Irradiated or excised lesions will be considered not measurable and will be monitored only for disease progression.

To qualify for PR, the sum of products of the perpendicular diameters of the existing extramedullary plasmacytomas must have decreased by at least 50%, and new plasmacytomas must not have developed. To qualify for disease progression, either the sum of products of the perpendicular diameters of the existing extramedullary plasmacytomas must have increased by at least 50% or a new plasmacytoma must have developed. In the cases where not all existing extramedullary plasmacytomas are reported, but the sum of products of the perpendicular diameters of the reported plasmacytomas have increased by at least 50%, this will also qualify as disease progression.

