#### **1.1.2 Secondary Objectives**

To describe the following in this study population:

- Safety and tolerability of once-weekly KRDI
- Minimal residual disease (MRD) after 4 cycles, at completion of consolidation (post-transplant) or induction (transplant-deferred) and at 24 months
- Complete response (CR + stringent CR) rate after 6 cycles in patients who undergo transplant, after 8 treatment cycles in transplant-deferred patients, and at 24 months for all patients- Overall response rate (ORR)
- Progression free survival (PFS)
- Overall survival (OS)
- Quality of life (QOL)

Exploratory

- Change in body composition
- PFS by MRD status

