Secondary Analysis: Secondary analyses will evaluate overall response rate, MRD rate, PFS and OS. Overall response rate will be percent of patients who achieve at least partial response (PR). Percent of patients achieving MR or better will also be collected as clinical benefit response. MRD rate after 4 cycles, at completion of induction, and at 24 months will be determined by deep sequencing of genomic deoxyribonucleic acid from bone marrow samples using rearranged Ig locus-specific primers (Adaptive, Seattle, WA). PFS will be defined as the time from first dose of study treatment to the first documentation of PD or death from any cause during study. OS will be defined as the time from first dose of study treatment to death from any cause. For responders, time to response (TTR) and duration of response (DOR) will be analyzed. TTR will be defined as the time from first dose of study treatment to the first documentation of response (either PR, very good partial response (VGPR) or CR, nCR, and sCR). DOR will be defined as the time from the first PR, VGPR, or CR to the first documentation of PD or death, whichever occurs earlier.

Response rates together with confidence intervals (CIs) will be provided. Kaplan-Meier curves will be used to characterize the time-to-event outcomes (PFS, OS, response duration) when there is censoring; univariate summary statistics will be provided for TTR. In addition, outcomes including median PFS and median OS will be calculated within sub-groups based on risk status (standard vs high) and MRD status (positive vs negative).

A 90% CI for the response rate will be constructed for evaluating the efficacy of KRDI. Kaplan-Meier curves will be constructed to characterize PFS, OS, and DOR. One sample standard inferences for PFS, OS, and DOR will be made accordingly.

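### Section 9.4 ends required plasmacytoma assessment at confirmed CR, although PD, PFS, DOR and 24-month CR all depend on it until progression

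*Combined protocol and SAP*

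**What the plan says.** Section 9.4 asks for local assessment of measurable extramedullary sites in patients with a history of plasmacytoma "or as clinically indicated during treatment until development of confirmed CR or confirmed disease progression". The same section lists as progression the case in which "a new plasmacytoma must have developed", without limiting this to the time before CR. It refers lesions that can only be assessed radiologically to the Schedule of Assessments.

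Elsewhere:

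- Section 9.1 has disease evaluated after each induction cycle and then at even-numbered cycles "during maintenance phase until disease progression". There is no stop at CR.
- The PD row of Table 15 includes "Definite development of new bone lesions or extramedullary plasmacytomas", and also definite growth of existing ones.
- The CR row of Table 15 requires "disappearance of all extramedullary plasmacytomas (if present at baseline").
- Section 12.1: "PFS will be defined as the time from first dose of study treatment to the first documentation of PD" or death. DOR ends at the same event.
- Section 1.1.2 lists the CR rate "and at 24 months for all patients" as a secondary objective.
- Tables 14A and 14B mark the extramedullary plasmacytoma row at screening only. Physical examination, SPEP/IFE and free light chains are marked through maintenance, treatment discontinuation and follow-up. Footnote 15 accepts clinical examination as a method for plasmacytomas.

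**The concern.** The plan counts an extramedullary relapse as progression at any time, but once CR is confirmed it no longer requires anyone to look for one at lesion level. Whether a patient's lesions are assessed then depends on that patient's response. Follow-up that depends on response is a known source of bias in time-to-event endpoints, because events are sought less actively in the patients who are doing best. The endpoints at stake are PFS, DOR and CR at 24 months. For the last of these, a patient could be credited with continuing CR although the plasmacytoma component of the definition had not been rechecked since CR was first confirmed.

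**Working it through.** The point rests on comparing texts. No figure in the plan is wrong because of it.

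**1. How long each provision runs**

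| Provision | Ends at |
|---|---|
| Section 9.4, assessment of measurable sites | confirmed CR or confirmed PD |
| Section 9.1, disease evaluation | PD |
| Table 15 and Section 9.4, new plasmacytoma as PD | no limit |
| Section 12.1, PFS and DOR | first documented PD or death |
| Section 1.1.2, late CR | 24 months |

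Only the first stops at CR.

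**2. What still operates after CR.** Physical examination, SPEP/IFE and free light chains remain scheduled. A relapse that is palpable, or that raises M-protein or light chains, would be caught by these. The gap is therefore a relapse that is neither palpable nor secretory.

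**3. Direction of bias.** Suppose such a relapse occurs at time T and is documented at T′, with T′ ≥ T, or is never documented. Recorded PFS and DOR are then at least as long as the true values, and a patient who has relapsed may still be counted as CR at 24 months. All three errors go upward.

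**4. Size.** The documents give no share of patients with plasmacytomas and no rate of extramedullary relapse, and they state no power for PFS or DOR. The bias cannot be computed. Only the number of patients whose lesion assessment would stop can be illustrated. Assume that 5% to 20% of patients have plasmacytomas, and that they reach CR after cycle 4 at the planning rate of 0.43:

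- 50 × 0.05 = 2.5 and 50 × 0.20 = 10 patients with plasmacytomas
- 2.5 × 0.43 = 1.1 and 10 × 0.43 = 4.3

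That is roughly 1 to 4 patients leaving assessment. They are not 1 to 4 missed relapses.

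**5. Primary endpoint.** The plan's design figures reproduce with the exact binomial:

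- 19 or more of 50: P(X ≥ 19 | 0.27) = 0.059 and P(X ≥ 19 | 0.43) = 0.804
- 17 or more of 45: 0.075 and 0.804

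Both agree with the stated 80% power. The stop applies only after CR is confirmed, so its effect on CR after 4 cycles is negligible.

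**6. The schedule row.** Section 9.4 sends imaging-only lesions to a row marked at screening only. For those lesions the plan sets no on-treatment time point, even before CR.

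**7. A secondary ambiguity.** Section 9.4 adds: "Irradiated or excised lesions will be considered not measurable and will be monitored only for disease progression". The CR row of Table 15 has no exception for irradiated lesions, and exclusion criterion 5 bars only radiotherapy within 7 days of enrollment, so such patients can enter. It is unclear whether a residual irradiated mass prevents CR. As a bound, assume exactly one patient is scored differently under the 19-of-50 rule. One extra CR gives a type I error of P(X ≥ 18 | 0.27) = 0.103. One CR lost gives power of P(X ≥ 20 | 0.43) = 0.714. Neither applies unless such a patient enrolls and meets every other CR criterion.

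**The case against.** The strongest reply is that the clause is harmless. CR requires every baseline plasmacytoma to be gone, so no measurable site remains to follow. Section 9.4 sets a minimum and forbids nothing afterwards, and relapse is still sought through examination and laboratory tests until progression. Much of this stands. A reader might infer that extramedullary relapse after CR is simply missed. The documents do not support that, because routine surveillance continues and clinical examination is an accepted method. The reply does not remove the conflict, however. Regrowth at an old site or a lesion at a new one is still PD, and CR at 24 months still has a plasmacytoma component to verify.

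A second reply is that the asymmetry is small. Because the schedule row is marked at screening only, patients short of CR have no scheduled on-treatment imaging either. The planned PFS subgroups are by risk and MRD status, not by CR, and PFS is only described by Kaplan-Meier. This also stands, and it limits the point to what Section 9.4 requires in its text. It also exposes the screening-only row as a gap in its own right.

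On irradiated lesions, a reader might infer that the plan contains two definitions of CR. It does not. Section 9.4 defines only PR and PD for plasmacytomas, and Table 15 is the sole CR definition. Excised lesions raise no question because they are already gone. Monitoring irradiated lesions for progression is what PFS needs, and that sentence has no stop at CR.

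**Conclusion.** The concern holds in a limited form. The stop at confirmed CR in Section 9.4 is inconsistent with how long Section 9.1, Table 15, PFS, DOR and the 24-month CR require extramedullary disease to be followed. The consequence is confined to complete responders whose relapse is neither palpable nor secretory, and its direction is upward. Its size is unknown, and the exposure of about 1 to 4 patients in the working rests wholly on an assumed prevalence and an assumed CR rate in that subgroup. The primary analysis is not materially affected by the stop. The status of a residual irradiated lesion is a separate ambiguity that needs clarifying, not an error in the CR definition.

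**What to change.** In Section 9.4, delete the reference to confirmed CR so that assessment of extramedullary sites continues until confirmed disease progression. State that after CR this is done by the physical examination already scheduled in Tables 14A and 14B, with imaging on suspicion. Then reconcile the cross-reference with the plasmacytoma row of those tables: either add on-treatment entries for lesions assessable only by imaging, or give the timing in Section 9.4 itself. Changing the clause alone would still leave the section pointing to a screening-only row.

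As a secondary clarification, add one sentence reconciling Section 9.4 with the CR row of Table 15 on whether a residual irradiated baseline lesion prevents CR, and settle it before responses are scored.

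The cost is a few sentences and one table row. The downside is occasional imaging in a few patients.
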